11.2.5.4 Vital Sign Measurements

The baseline vital sign measurement will be defined as the last value prior to or on the day of the first dose of CO-1686. The on-treatment period will be defined as the day after the first dose of CO-1686 to 28 days after the last dose of CO-1686. Vital sign measurements collected during the on-treatment period will be included in the summary tables. The vital sign measurements collected after the on-treatment period will only be presented in the data listings.

The summary of vital sign data will include descriptive statistics (N, mean, standard deviation, minimum, median, and maximum) of the maximum, minimum, and last value during the on-treatment period. Summaries using descriptive statistics of the change from baseline to the maximum, minimum, and last value during the on-treatment period will also be given.

11.2.5.5 12-lead Electrocardiograms

ECG intervals will be stratified into categories indicative of potential clinical significance. Each patient's maximum QT and QT_C intervals from the pretreatment visit and treatment period visits will be classified as ≤ 450 msec, > 450 msec to ≤ 480 msec, > 480 msec to ≤ 500 msec, and > 500 msec. For each patient's maximum change from the pretreatment ECG visit for QT and QT_C, intervals will be classified into < 30 msec, ≥ 30 msec to < 60 msec, and ≥ 60 msec. The number and percentage of patients in each classified category will be presented. Additional endpoints will include abnormal T waves and U waves and other ECG intervals and diagnostic parameters.

Descriptive statistics will be used to summarize other ECG parameters of PR, QRS, QT, and RR interval, and the corresponding changes from pretreatment ECG visit at each time point. Plots of the mean QT/QT_C over time will be provided.

11.2.5.6 Other Safety Measurements

Concomitant medications/procedures will be tabulated and summarized.

11.2.6 Exploratory Endpoints—Pharmacodynamic Analysis

An exploratory pharmacodynamic endpoint is the detection and quantification of mutant EGFR ctDNA in blood collected at baseline and with every tumor assessment. The presence of both the activating mutation and T790M at baseline and subsequent time points will be presented both as copies/mL plasma and mutant allele percentages. In addition, the relationship between T790M detected in tumor compared with that detected in blood will be explored. This will involve determining the sensitivity, specificity, positive and negative predictive values with 95% CIs of blood with respect to tumor assuming that EGFR mutational status in tumor is a true reflection of

tumor biology. The ctDNA from blood collected at these time points may also be assessed to identify biomarkers of response or resistance to EGFR-targeted therapy.

11.3 Sample Size Considerations

Cohort A: Approximately 125 patients will be enrolled. The ORR will be presented with 95% CIs. [Table 11-1](#) provides the 95% CIs for observed response rates of 30%, 40%, and 50% assuming a total of 125 patients.

Table 11-1: Confidence Intervals for Observed Response Rates

Number of Patients	ORR (%) [95% CI]
125	30 [22, 39]
125	40 [31, 49]
125	50 [41, 59]

Cohort B: Approximately 100 patients will be enrolled with the aim to include approximately 40 response evaluable T790M-negative NSCLC patients. To be response evaluable, patients should have received at least one cycle of therapy, and have had their disease re-evaluated by radiological assessment.

An exact binomial test with a nominal 0.10 2-sided significance level will have approximately 90% power to detect the difference between a null hypothesis response rate of 20% and a clinically meaningful response rate of 40% when the sample size is 40.

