Statistical Procedures	
Analysis Populations
 
 • Tumor evaluable population—all patients who received at least 1 dose of CO-1686, have at least 1 measurable tumor lesion at baseline and have at least 1 post-baseline tumor assessment as assessed by IRR (Cohort A) or investigator assessment (Cohort B) • Safety population—all patients who have received at least 1 dose of CO-1686 
Sample Size Justification
 
Cohort A: Approximately 125 patients will be enrolled. The ORR will be presented with 95% confidence intervals (CIs). The following table provides the 95% CIs for observed response rates of 30%, 40%, and 50% assuming a total of 125 patients.
 
  
 Confidence Intervals for Observed Response Rates	
 
 Number of Patients	ORR (%) [95% CI]	
   
 125	30 [22, 39]	
 
 125	40 [31, 49]	
 
 125	50 [41, 59]	
  
 
Cohort B: Approximately 100 patients will be enrolled with the aim to include approximately 40 response evaluable, centrally confirmed T790M-negative NSCLC patients. To be response evaluable, patients should have received at least one cycle of therapy, and have had their disease re-evaluated by radiological assessment.
 
An exact binomial test with a nominal 0.10 2-sided significance level will have approximately 90% power to detect the difference between a null hypothesis response rate of 20% and a clinically meaningful response rate of 40% when the sample size is 40.
 
Efficacy Analysis
 
The ORR in both centrally confirmed T790M-positive and centrally confirmed T790M-negative patients will be summarized separately with frequencies and percentages. The DR for complete response (CR) and partial response (PR) for both centrally confirmed T790M-positive and centrally confirmed T790M-negative patients will be summarized separately with descriptive statistics (N, mean, standard deviation, median, minimum, and maximum) as well as categorically.
 
DCR is defined as the percentage of patients who have achieved CR, PR, and stable disease (SD). Kaplan-Meier methodology will be used to summarize PFS and OS.
 
Safety Analyses
 
Data from all patients who receive 1 or more doses of CO-1686 will be included in the safety analyses. AEs, clinical laboratory information, vital signs, ECOG performance status and concomitant medications/procedures will be tabulated and summarized.
 
Population PK
 
Sparse blood sampling for POPPK analyses will be conducted in all patients treated with CO-1686. A specific POPPK data analysis plan will be developed
	Confidence Intervals for Observed Response Rates		Number of Patients	ORR (%) [95% CI]	125	30 [22, 39]	125	40 [31, 49]	125	50 [41, 59]

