11 STATISTICAL METHODS

11.1 Analysis Populations

The following analysis populations are defined for the study:

Tumor Evaluable Population—all patients who received at least 1 dose of CO-1686, have at least 1 measureable tumor lesion at baseline, and have at least 1 post-baseline tumor assessment as determined by the IRR.

Safety Population—all patients who have received at least 1 dose of CO-1686.

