11.2.4 Efficacy Analyses

The efficacy endpoints will be evaluated using RECIST Version 1.1 for the tumor evaluable population. Separate analyses will be performed for the assessments from the investigator and the independent reviewer.

PFS and OS will also be presented for the safety population.

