11.2.4.1 Primary Endpoint

The primary endpoint of the study will be ORR according to RECIST Version 1.1. For Cohort A, ORR will undergo independent radiology review (IRR) and in Cohort B, scans will be assessed by IRR if needed as a supporting analysis.

The ORR is the best overall response recorded from the start of the treatment until disease progression or recurrence.

The frequency and percentages of patients with a best overall response of CR, PR, SD, or progressive disease (PD) will be summarized.

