11.2.4.2 Secondary Efficacy Endpoints

BEST OVERALL RESPONSE

The frequency and percentages of best overall responses of CR, PR, SD, or PD will be summarized separately for T790M-positive and T790M-negative patients, and by dose.

DURATION OF RESPONSE

DR for CR and PR will be measured from the date that any of these best responses is first recorded until the first date that PD is objectively documented. DR will be summarized separately for T790M-positive and T790M-negative patients, and by dose, using descriptive statistics (N, mean, standard deviation, median, minimum, and maximum) as well as categorically. For patients who continue treatment post-progression, the first date of progression will be used for the analysis.

DISEASE CONTROL RATE

DCR is defined as the percentage of patients who have achieved CR, PR, and SD lasting at least 12 weeks.

PROGRESSION-FREE SURVIVAL

PFS will be calculated as 1+ the number of days from the first dose of study drug to documented radiographic progression or death due to any cause, whichever occurs first. Patients without a documented event of radiographic progression will be censored on the date of their last adequate tumor assessment (i.e., radiologic assessment) or date of first dose of study drug if no tumor assessments have been performed.

For patients who continue treatment post-progression, the first date of progression will be used for the analysis of PFS.

OVERALL SURVIVAL

OS will be calculated as 1+ the number of days from the first dose of study drug to death due to any cause. Patients without a documented date of death will be censored on the date the patient was last known to be alive.

POPULATION PK ANALYSES

Sparse blood sampling for POPPK analyses will be conducted in all patients treated with CO-1686. A specific POPPK data analysis plan will be developed and will outline the detailed approach to data handling, model development and diagnostics, individual model parameter estimation, exploration of covariate effects, and final model evaluation techniques.

QUALITY OF LIFE

QoL will be measured using the EORTC QLQ-C30, EORTC QLQ-LC13, and the DLQI.^{12,13}

The EORTC questionnaires will be scored using the published scoring algorithms provided by the EORTC. For each item or scale, a linear transformation will be applied to standardize the raw score to a range from 0 to 100. A high scale score represents a higher response level.

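### Cohort B's stated power of about 90% is 87.1% under the usual exact binomial tests at n = 40, and the Cohort B analysis population needs reconciling

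*Protocol*

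**What the plan says.** ORR in T790M-negative patients is part of the primary objective (Protocol 4.1.1). Cohort B is sized for it in 11.3: about 100 patients enrolled, to yield about 40 response evaluable T790M-negative patients. The power statement begins "An exact binomial test with a nominal 0.10 2-sided significance level will have approximately 90% power to detect the difference between a null hypothesis", with a null rate of 20%, an alternative of 40% and a sample size of 40. The Synopsis (Sample Size Justification) repeats it: "exact binomial test with a nominal 0.10 2-sided significance level will have approximately 90% power".

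The efficacy sections are descriptive:
- Synopsis, Efficacy Analysis: "The ORR in both centrally confirmed T790M-positive and centrally confirmed T790M-negative patients will be summarized separately with frequencies and percentages".
- 11.2.4.1: "The frequency and percentages of patients with a best overall response of CR, PR, SD, or progressive disease (PD) will be summarized".
- 11.2.4.2: "The frequency and percentages of best overall responses of CR, PR, SD, or PD will be summarized separately for T790M-positive and T790M-negative patients".

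On the population:
- 11.3: "To be response evaluable, patients should have received at least one cycle of therapy, and have had their disease re-evaluated by radiological assessment".
- 11.2.4: "The efficacy endpoints will be evaluated using RECIST Version 1.1 for the tumor evaluable population".
- 11.1 defines the tumor evaluable population by at least one dose, a measurable baseline lesion and a further condition: "have at least 1 post-baseline tumor assessment as determined by the IRR".
- The Synopsis (Analysis Populations) gives the same definition but uses independent radiology review (IRR) for Cohort A and investigator assessment for Cohort B.
- 4.2.1, 5.1.2, 9.5.2.1 and 11.2.4.1 make IRR in Cohort B a supporting analysis, done only when needed.

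**The concern.** The power sentence names an exact test and gives every input, so its figure can be checked directly. Binomial counts are discrete. An exact test at a nominal 0.10 therefore usually attains less than 0.10, and its power can fall below that of a smooth approximation. If the printed figure does not belong to the named test, the study report will repeat a power that this test did not have, with no stated cutoff for judging the result.

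The population matters because the cutoff depends on the denominator. 11.3 counts patients with at least one cycle and a radiological re-evaluation. 11.2.4 points to a set that needs only one dose and a post-baseline assessment. Read literally, 11.1 would leave Cohort B with no tumor evaluable patients if IRR were never done there.

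**Working it through.** **Inputs**, all from Protocol 11.3 and the Synopsis: exact binomial test, two-sided 0.10, p0 = 0.20, p1 = 0.40, n = 40. The 40 are already evaluable patients, so no dropout allowance enters.

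**Attempt to reproduce 90%.** The uncorrected normal approximation is Phi[(sqrt(n)(p1 − p0) − 1.645·sqrt(p0(1 − p0))) / sqrt(p1(1 − p1))] = Phi[(1.265 − 0.658)/0.490] = Phi(1.239) = 89.2%. This is close to the printed figure but is not the test named. Other approximations at the same two-sided level give 85.9% (with continuity correction), 87.5% (arcsine) and 82.6% (Wald, alternative variance).

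**The exact test.** Let X be binomial with n = 40.

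| Quantity | p = 0.20 | p = 0.40 |
|---|---|---|
| P(X ≥ 12) | 0.0875 | 0.9291 |
| P(X ≥ 13) | 0.0432 | 0.8715 |
| P(X ≤ 3) | 0.0285 | < 0.0001 |
| P(X ≤ 2) | 0.0079 | < 0.0001 |

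*Equal-tailed convention* (at most 0.05 per tail): 0.0875 is too large and 0.0432 is allowed, so the upper cutoff is 13. The lower region is X ≤ 3, because P(X ≤ 4) = 0.0759 exceeds 0.05.

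*Minimum-likelihood convention* (sum of all outcomes no more likely than the one observed):
- At 13 responses: p = 0.0432 + 0.0285 = 0.0717, reject.
- At 12 responses: p = 0.0875 + 0.0285 = 0.1160, do not reject.

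For comparison, the doubled-tail p-values are 0.0865 at 13 and 0.175 at 12. Both conventions give the region X ≤ 3 or X ≥ 13:
- attained two-sided level = 0.0432 + 0.0285 = **0.0717**
- power at 40% = **87.1%**, with a negligible contribution from the lower tail
- shortfall = 90 − 87.1 = 2.9 points

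The Clopper-Pearson 90% lower limit agrees with the equal-tailed rule: 0.183 at 12/40 and 0.204 at 13/40.

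**Other exact regions.** The asymmetric region X ≤ 2 or X ≥ 12 has size 0.0079 + 0.0875 = 0.0954, within 0.10, and power 92.9%. It belongs to neither usual convention.

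**Near n = 40**, since the target is itself approximate:

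| n | Equal-tailed: cutoff, power | Minimum-likelihood: cutoff, power |
|---|---|---|
| 37 | 13, 77.8% | 12, 86.7% |
| 38 | 13, 81.4% | 13, 81.4% |
| 39 | 13, 84.5% | 13, 84.5% |
| 40 | 13, 87.1% | 13, 87.1% |
| 41 | 14, 82.2% | 13, 89.5% |
| 42 | 14, 85.1% | 13, 91.4% |
| 43 | 14, 87.6% | 14, 87.6% |
| 44 | 14, 89.8% | 14, 89.8% |

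The two conventions coincide at 40 but differ at 37, 41 and 42. A named convention therefore matters once the realised number is not 40.

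**Population.** Placed together, the texts conflict in two respects. On the assessor, 11.1 requires IRR for everyone, while the Synopsis and the endpoint text rely on the investigator for Cohort B. On exposure, 11.3 requires one cycle, while 11.1 and the Synopsis require one dose.

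**The case against.** The source hedges: power, sample size and level are each given as approximate or nominal. A power of 87% is adequate for a Phase 2 cohort, and exact power is saw-toothed, so a 3-point gap at one n has little weight. This stands, and it limits the point to a correction of the text.

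Several stronger readings are tempting but are not supported:

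- *That no exact test at n = 40 reaches 90%, or that a cutoff of 12 must break the 0.10 level.* It fails under both usual conventions, but the region X ≤ 2 or X ≥ 12 is a valid exact 0.10 region with 92.9% power. The protocol names no tail convention.
- *That the figure came from a normal approximation.* The 89.2% is suggestive, but the documents do not say how the figure was obtained.
- *That the test is missing from the plan.* 11.3 lies within the Statistical Methods section and states the test, null and level. Cohort A's 95% interval is likewise stated there and not in 11.2.4.1. The gap is mostly one of placement.
- *That the SAP is at fault.* The SAP supplied covers the protocol through Amendment 3 and describes only T790M-positive patients.
- *That the assessor for Cohort B is unknown.* The Synopsis and the endpoint text make investigator assessment the evident intent; 11.1 is the outlier.
- *That the choice of population would reverse the conclusion.* An example can be built: 13/40 rejects 20%. If three early stoppers with a scan and no response are added, 13/43 does not (p = 0.147 doubled tail, 0.124 minimum likelihood). It sits on the boundary by construction, and nothing in the documents supports those numbers.

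Finally, development has been discontinued and no more patients will be enrolled (Protocol 3.1 and Appendix C). A rule chosen now, in an open-label study, could be informed by known responses. This also stands and governs how the fix must be labelled.

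**Conclusion.** The point holds as a minor correction. Under the equal-tailed or minimum-likelihood exact test, n = 40 gives a cutoff of 13, an attained two-sided level of 0.072 and power of 87.1%, not about 90%. This rests on the protocol's own inputs and on using one of those two conventions. It does not show that Cohort B is too small.

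The population conflict is separate and real. 11.1 cannot be applied to Cohort B as written unless IRR is done there, and 11.3 sizes on a different set from the one that 11.2.4 analyses. Its effect on the result cannot be quantified from the documents.

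**What to change.** 1. In 11.3 and the Synopsis, state: n = 40; reject 20% if 13 or more respond; attained two-sided level 0.072; power about 87% at 40%. Leave the sample size unchanged.
2. Align 11.1 with the Synopsis, using investigator assessment for Cohort B. Name either the tumor evaluable or the response evaluable set as primary for the T790M-negative ORR, and the other as a sensitivity analysis.
3. Carry the 11.3 test into 11.2.4.1 with one named tail convention and a matching 90% exact interval. If equal-tailed with Clopper-Pearson is chosen, the cutoff is 13 for n = 37 to 40 and 14 for n = 41 to 44.
4. Label any newly chosen convention, cutoff or population as specified after enrolment, in the plan and in the study report.

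The cost is wording in 11.1, 11.2.4.1, 11.3 and the Synopsis, and a slightly less favourable power figure. No patients or data are added.

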12 PATIENT DISPOSITION

12.1 Patient Discontinuations

A patient must be discontinued from protocol-prescribed therapy if any of the following apply:

- Consent withdrawal at the patient's own request or at the request of their legally authorized representative
- Progression of patient's underlying disease, except as noted in [Section 5.1.2](#)
- Any event, adverse or otherwise, that, in the opinion of the investigator, would pose an unacceptable safety risk to the patient
- An intercurrent illness that, in the opinion of the investigator, would affect assessments of the clinical status to a significant degree and requires discontinuation of therapy
- A positive pregnancy test at any time during the study
- Noncompliance as described in [Section 7.7](#)
- Investigator decision

In addition, the sponsor may discontinue the trial early for any of the reasons noted in [Section 13.6](#).

The sponsor (or designee) should be notified of all study terminations as soon as possible. The date and reason for cessation of PO CO-1686 must be documented in the eCRF and source documents.

To the extent possible, end-of-treatment procedures should be performed on all patients who receive CO-1686. The End-of-Treatment Visit should occur 28 (\pm 7) days following the last dose of CO-1686. After stopping protocol-specified treatment, all patients will remain in the study and will be followed for safety (through 28 days after last dose; those with ongoing SAEs will be followed until either resolution or stabilization has been determined), for disease progression if the patient discontinues treatment prior to progression (every 8 ± 1 weeks until disease progression), and for survival status and subsequent NSCLC therapies (at approximately 2-monthly intervals until death or sponsor decision).

13 STUDY ADMINISTRATION

13.1 Regulatory and Ethical Considerations

This study will be conducted in compliance with the protocol; Good Clinical Practices (GCPs), including International Conference on Harmonization (ICH) Technical Requirements for Registration of Pharmaceuticals for Human Use Guidelines; FDA regulatory requirements; and in accordance with the ethical principles of the Declaration of Helsinki.

13.1.1 Regulatory Authority Approvals

The sponsor or designee will submit the study protocol plus all relevant study documents to concerned regulatory agencies for approval prior to the study start. No patient will be admitted to the study until appropriate regulatory approval of the study protocol has been received.

Each investigator must complete a Form FDA 1572 or equivalent and provide the completed form according to written instructions to the sponsor (or designee). Each investigator must submit to the sponsor (or designee) financial disclosure information according to national law and/or local regulations.

US-generated data will be handled in accordance with the Health Information Portability and Accountability Act (HIPAA). The trial will be registered at www.clinicaltrials.gov using the Protocol Registration System.

13.1.2 Independent Ethics Committee/Institutional Review Board

This protocol and any material to be provided to the patient (such as advertisements, patient information sheets, or descriptions of the study used to obtain informed consent) will be submitted by the investigator to an IEC/IRB. This also applies to protocol amendments.

Clovis will supply relevant data for the investigator to submit the study protocol and additional study documents to the IEC/IRB. The principal investigator will submit the study protocol for review and approval by an IEC/IRB, according to national law and/or local regulations, and will provide the IEC/IRB with all appropriate materials.

Verification of the IEC's/IRB's unconditional approval of the study protocol and the written ICF will be transmitted to Clovis. This approval must refer to the study by exact study protocol title and number, identify the documents reviewed, and state the date of the review.

No patient will be admitted to the study until appropriate IEC/IRB approval of the study protocol has been received, the investigator has obtained the signed and dated ICF, and the sponsor is notified.

The principal investigator will submit appropriate reports on the progress of the study to the IEC/IRB at least annually in accordance with applicable national law and/or local regulations and in agreement with the policy established by the IEC/IRB and sponsor.

The IEC/IRB must be informed by the principal investigator of all subsequent study protocol amendments and of SAEs or SUSARs occurring during the study that are likely to affect the safety of the patients or the conduct of the study.

13.2 Confidentiality of Information

The investigator must assure that patients' anonymity is strictly maintained and that their identities are protected from unauthorized parties. Only patient initials and an identification code (i.e., not names) should be recorded on any form submitted to the sponsor and the IEC/IRB. The investigator must keep logs on screened and enrolled patients. In addition, the investigator must have a list where the identity of all treated patients can be found.

The investigator agrees that all information received from Clovis, including, but not limited to, the Investigator's Brochure, this protocol, eCRFs, the protocol-specified treatment, and any other study information, remain the sole and exclusive property of the sponsor during the conduct of the study and thereafter. This information is not to be disclosed to any third party (except employees or agents directly involved in the conduct of the study or as required by law) without prior written consent from the sponsor. The investigator further agrees to take all reasonable precautions to prevent the disclosure by any employee or agent of the study center to any third party or otherwise into the public domain.

